9.2.1 Duration of the study

The study will be conducted in 3 waves during 3 consecutive years.

The rationale for conducting the 3 waves when treatment patterns are evaluated across 3 different cohorts of Praluent prescribers and their patients is as follows:

- To confirm the effectiveness of the SmPC dosing recommendations risk minimization measures observed in the repeated waves.
- To observe the trend in practice over time, if any, by comparing findings across the 3 waves.
- Using 3 waves will also allow getting preliminary data available sooner, with the earliest availability at the end of the first wave.

After the first Praluent prescription identified during the eligibility period (Mar to Jun 2017 for Wave 1, Jul 2017 to Jun 2018 for Wave 2, and Jul 2018 to Jun 2019 for Wave 3), the observation period will last 6 months for each patient: from their first prescription to 6 months later, at the latest until the end of December 2017, 2018 and 2019, respectively.

After the end of the 6-month observation period, submission of appropriate documentation to Regulatory Authorities (if applicable according to local regulations) and/or Ethics Committees will be performed, in parallel, the physicians will be enrolled and informed of the main purpose of the study and upon all relevant approvals are obtained, the patients will be selected up to the first quarter (Q1) of 2019, 2020, and 2021 following the observation period, respectively.

The data will be collected retrospectively from the second quarter (Q2) 2018 to Q1 2019 in Wave 1, from Q1 2019 to Q1 2020 in Wave 2 and from Q1 2020 to Q1 2021 in Wave 3, respectively. Please see details in Figure 1 and Figure 2.

Figure 1 - Annual study progress in Wave 1

Wave 1

[figure not shown]
[figure not shown]

Figure 2 - Annual study progress in Waves 2 and 3

Waves 2 and 3

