9.2.3 Analysis populations

The analysis population will consist of all patients included in the study and meeting all inclusion criteria. This population will be the eligible population.

Physicians who included at least one patient in the patient analysis population will be part of the physicians' analysis population.

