9.3.4 Discontinuation of Praluent, if relevant

- 1. Date of discontinuation;
- 2. Reason for discontinuation:
 - (1) Description of reason, if available.
 - (2) Unspecified.

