9.3.7 Adverse events

An adverse event (AE) is any untoward medical occurrence in a patient or in a clinical investigation subject administered a pharmaceutical product, and which does not necessarily have a causal relationship with that treatment. An adverse event can thus be any abnormal laboratory finding, symptom or disease temporally associated with the use of a medicinal (investigational) product, whether or not caused by that product.

Adverse events will be collected from the initiation of Praluent until the end of the 6-month observational period with the following details:

- 1. Nature of AE, such as hospitalization, onset of new disease, a new symptom, worsening of an existing condition, or lab abnormalities...
- 2. Start date/end date and outcome
- 3. Action taken with Praluent, if any: discontinuation, delay, or dose change.

9.3.8 Date on which the patient is no longer managed by the treating physician

Date on which the patient is no longer managed by the treating physician will be collected, if it is applicable.

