9.4 DATA SOURCES

As soon as the ICF is signed and dated by the patient, the data abstraction can be started. Hence, data from medical records (either EMRs or paper source files) for each participating patient will be extracted and completed by site personnel and/or trained and authorized external abstractors using an e-CRF.

For patients in whom Praluent will be initiated by a given physician, and who will then be followed by another physician, all efforts will be made to collect data from these multiple caregivers.

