9.7.2 Secondary analysis

A. The starting dose of Praluent

- 1. The proportion of patients for whom Praluent is started at 75 mg Q2W, 150 mg Q2W, or 300 mg Q4W:
 - (1) In the whole analysis population;
 - (2) According to baseline LDL-C level:
 - a) <70 mg/dL (<1.81 mmol/L),
 - b) 70 to < 100 mg/dL (2.59 mmol/L),
 - c) 100 to < 130 mg/dL (3.37 mmol/L),
 - d) 130 to < 160 mg/dL (4.14 mmol/L),
 - e) 160 to < 190 mg/dL (4.92 mmol/L),
 - f) $\geq 190 \text{ mg/dL } (4.92 \text{ mmol/L}).$
 - (3) According to diagnosis of heterozygous familial hypercholesterolemia, ASCVD, diabetes and chronic kidney disease.
- 2. Mean baseline LDL-C level by starting dose.

B. Modification of the dosage regimen of Praluent

- 1. The proportion of patients for whom the dosage regimen of Praluent is modified during the 6-month observational period.
 - An estimate of the event rate at the end of the 6 months by a Kaplan-Meier approach.
- 2. Among the patients for whom the dosage regimen of Praluent is modified from the initial dose during the 6-month observational period:
 - (1) The median time to dosage regimen modification estimated using time-to-event approach (Kaplan Meier methodology),
 - (2) The mean LDL-C levels prior to and at least 4 weeks after the dosage regimen modification respectively,
 - (3) The proportion of patients for whom the dosage regimen is adjusted back to the initial regimen.

C. Timing of LDL-C tests

- 1. The mean time from the first prescription of Praluent to a LDL-C test in patients having a LDL-C test after initiation of Praluent and the median time estimated using a Kaplan-Meier approach in all patients having a follow-up,
- 2. The mean time from a dosage regimen modification to a LDL-C test in patients having a LDL-C test after initiation of Praluent and the median time estimated using a Kaplan-Meier approach in all patients having a follow-up.

D. Discontinuation of Praluent

- 1. Proportion of patients for whom Praluent is discontinued during the 6-month observational period after index date:
 - (1) Overall,
 - (2) By starting dose.
- 2. Among the patients for whom Praluent is discontinued:
 - (1) Proportion of patients on each dose regimen (75 mg Q2W versus 150 mg Q2W versus 300 mg Q4W) prior to discontinuation,
 - (2) Proportions of patients who had LDL-C <25 mg/dL (0.65 mmol/L) and <15 mg/dL (0.39 mmol/L) prior to discontinuation, respectively,
 - (3) Proportion of patients according to each reason for discontinuation, if available,

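### Protocol 9.7.2 D.1 plans 6-month discontinuation only as a crude proportion, without the Kaplan-Meier estimate that B.1 adds for dose modification, so it reads modestly low where records end early

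*Protocol*

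**What the plan says.** - **Discontinuation.** Protocol 9.7.2 D.1 plans "Proportion of patients for whom Praluent is discontinued during the 6-month observational period after index date", overall and by starting dose. No Kaplan-Meier estimate is listed under D.
- **Dose modification.** Protocol 9.7.2 B.1 plans a crude 6-month proportion and adds "An estimate of the event rate at the end of the 6 months by a Kaplan-Meier approach".
- **Timing of LDL-C tests.** Protocol 9.7.2 C plans, beside the mean, "the median time estimated using a Kaplan-Meier approach in all patients having a follow-up".
- **Event date.** Protocol 9.3.4 collects "Date of discontinuation".
- **Leaving care.** Protocol 9.3.8 states: "Date on which the patient is no longer managed by the treating physician will be collected, if it is applicable".
- **Denominator.** Protocol 9.2.3 states: "The analysis population will consist of all patients included in the study and meeting all inclusion criteria". Neither the inclusion nor the exclusion criteria set a minimum length of follow-up.
- **Nominal follow-up.** Protocol 9.2.1 states that "the observation period will last 6 months for each patient".
- **Change of physician.** For patients started by one physician and followed by another, Protocol 9.4 promises that "all efforts will be made to collect data from these multiple caregivers".

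**The concern.** The protocol foresees that some patients will move away from the treating physician within the 6 months, and it collects the date. It uses Kaplan-Meier for two neighbouring outcomes, but leaves discontinuation with the crude proportion alone.

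Take a patient who moves on at month 2, whose later records cannot be obtained and who has no recorded stop. Under 9.2.3 and D.1 this patient counts in the denominator and not in the numerator, which amounts to treating 2 observed months as 6 months without a stop. Each such patient can only lower the estimate. The error has a known direction and does not shrink as the sample grows. At stake is the level of the 6-month discontinuation figure, overall and within each starting dose.

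**Working it through.** **Inputs**

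- From the protocol: 6 months of nominal follow-up (9.2.1), all eligible patients as denominator (9.2.3), and a total of about 454 to 574 patients (9.5.2).
- Not in the protocol, so assumed: the true 6-month discontinuation risk P (10% to 30%) and the share L whose records end before month 6 and are not recovered from a later caregiver (5% to 30%).

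**1. The plan's own figures.** The protocol gives no figure for discontinuation or loss, so there is none to reproduce. The precision basis can be checked: exact 95% limits at 5% come to 3.19 to 7.43 for N = 454 and 3.37 to 7.11 for N = 574. Protocol Table 3 gives 3.2 to 7.4 and 3.4 to 7.1, which agrees.

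**2. Expected crude proportion, loss spread over the 6 months.** With constant, independent hazards and the 6 months as the time unit, a = -ln(1 - P) and b = -ln(1 - L):

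crude = a/(a + b) x [1 - exp(-(a + b))]

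For P = 15%, a = 0.1625:

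- L = 5%: b = 0.0513; 0.1625/0.2138 x (1 - 0.85 x 0.95) = 0.760 x 0.1925 = 14.6%
- L = 10%: b = 0.1054; 0.1625/0.2679 x (1 - 0.85 x 0.90) = 0.607 x 0.235 = 14.3%
- L = 20%: b = 0.2231; 0.1625/0.3857 x (1 - 0.85 x 0.80) = 0.421 x 0.32 = 13.5%

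The understatement is 0.4 to 1.5 points.

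**3. Less favourable timing: all loss at month 1.** Here crude = (1 - L) x P + L x [1 - exp(-a/6)]. Both cases side by side:

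| True P | L | Crude, loss spread | Crude, loss at month 1 |
|---|---|---|---|
| 10% | 10% | 9.50% | 9.17% |
| 10% | 20% | 8.98% | 8.35% |
| 20% | 5% | 19.51% | 19.18% |
| 20% | 10% | 19.02% | 18.37% |
| 20% | 20% | 18.00% | 16.73% |
| 20% | 30% | 16.93% | 15.10% |
| 30% | 20% | 27.07% | 25.15% |

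**4. Against sampling error.** At 20%, the exact 95% CI half-width is (23.98 - 16.42)/2 = 3.78 points for N = 454 and (23.51 - 16.80)/2 = 3.35 points for N = 574, taking the unrounded limits. At P = 20% the bias with 10% loss is 0.98 points (spread) or 1.63 points (month 1), well inside these. With all loss at month 1 it is 3.27 points at L = 20%, close to the half-width, and 4.90 points at L = 30%, beyond it.

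**5. Does Kaplan-Meier remove the bias?** A simulation with N = 574, P = 20%, L = 10% and 4,000 runs gave a mean of 19.98% for Kaplan-Meier and 19.00% for the crude proportion. Under independent loss, it does.

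**The case against.** Four objections deserve an answer.

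*Nothing in D.1 contradicts B.1.* This stands. B.1 leads with a crude proportion of the same form. A reader might infer that the discontinuation and dose modification figures cannot be compared; the text does not support this, because the two crude proportions are directly comparable. What D lacks is the companion estimate.

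*Leaving the treating physician is not the same as losing the data.* This also stands. Section 9.4 seeks records from later caregivers, and 9.2.4.1 and 9.9 say that availability of 6-month data is checked at site selection. The bias arises only for patients whose records really end early, and they may be few. It also follows that censoring everyone at the 9.3.8 date would be wrong, since it would discard stops recorded by later caregivers.

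*This is detail for the SAP.* It stands in part. Section 9.7 presents itself as the specification for the SAP, which is not at hand and may add the estimate. But the protocol itself chose the estimators, adding Kaplan-Meier under B and C and not under D, so an SAP that follows it keeps the gap.

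*The effect is small, assumed and secondary.* This stands and limits the weight of the point, but it does not remove the bias.

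Two further inferences are tempting. One is that differences in discontinuation by starting dose reflect unequal follow-up; nothing in the protocol suggests that loss differs by dose. The other is that the same sums apply to very low LDL-C; that outcome is seen only at discrete tests, so the constant-hazard model does not carry over.

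**Conclusion.** The point holds as a modest improvement to a secondary, descriptive analysis. D.1 fixes a crude proportion over all eligible patients, and that figure is too low whenever records end early without a recorded stop. That such patients count as not discontinued follows from the denominator in 9.2.3; the protocol does not say so outright.

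The size rests on assumed inputs: 0.4 to 1.5 points for a true 15% at 5% to 20% loss, with constant hazards and loss unrelated to stopping. For the pooled sample this is below sampling error, which the bias approaches or passes only at roughly 20% to 30% early loss. If leavers stop treatment more often than those who stay, the crude figure is further off than shown, and Kaplan-Meier would also read low.

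**What to change.** In Protocol 9.7.2 D.1 (and in the SAP, if it is not already there):

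1. Keep the crude proportion.
2. Add, overall and by starting dose, a Kaplan-Meier estimate of 6-month discontinuation with 95% CI.
3. Censor at the end of available records or month 6, whichever is earlier. Use the 9.3.8 date as the end of records only when no later-caregiver data were obtained under 9.4.
4. State how deaths are handled.
5. Report the number of patients with incomplete follow-up.
6. Note beside the estimate that it assumes leaving care is unrelated to stopping treatment and may still understate discontinuation.

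The cost is one extra output using a method already planned. The discontinuation and leaving-care dates are already collected. For patients with later-caregiver data, the end of the records obtained is not a listed variable in 9.3 and would need a short derivation rule. The estimate can be produced for all three waves in the final report.

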9.7.3 Sensitivity analysis regarding the physicians selection

Physicians who are/were involved in an observational study on Praluent are allowed to participate in this study. If these physicians provided at least 15% of the patients in this study then, to assess if this constitutes a bias, all analyses will be conducted separately in patients who were managed by them and in patients who were managed by physicians who had never participated in an observational study on Praluent.

The MAH plans to assess the representativeness of study sample with respect to the level of prescription a posteriori in the analysis phase. This analysis will stratify data by physician usage patterns to understand how they might impact dosing recommendations and assess the effectiveness of the Praluent dosing recommendations with regard to the occurrence of low LDL-C levels and will consist of:

a) The MAH will be collecting information on the level of prescription via a case report form (CRF) on the enrolled physicians. The final selected study sample of Praluent prescribers will be compared to the population of Praluent prescribers

identified from the Xponent or equivalent databases, with respect to the level of prescription.

- b) If the groups (ie, high, medium or low prescribers) are not balanced in a similar way, and if representativeness cannot be assumed, results will be presented by stratifying the level of prescription in each interim report and the final study report.
- c) As deemed appropriate, statistical techniques will be applied in the analysis phase to ensure the groups are representative with respect to the level of prescription.

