9.2.4 Modalities of recruitment

9.2.4.1 Physician selection

National prescriber databases containing health care professionals' information and their prescribing information, will be used to identify sites in each selected country.

For each wave, a 3-step process will be followed: identification from prescription database(s), selection, and remote recruitment.

• Identification: sites' prescribing volume of Praluent will be identified via Xponent database (or equivalent databases of prescriptions received in pharmacies). Additional databases will be selected in each country of interest to better identify the prescribers. Then, physicians/practices/institutions (depending on each country's data privacy limitations) with Praluent prescription during the eligibility period will be identified via OneKey database (or similar databases of physicians and/or hospital information). The prescribing physicians will be specialists (mainly, but not limited to, cardiologists, endocrinologists and internists) and/or general practitioners.

The clusters and physicians that have the highest likelihood of having prescribed Praluent and of participating in the study will be contacted regardless of their level of prescription. Representativeness of study sample with respect to the prescription level will be assessed a posteriori in the analysis phase (details in Section 9.7.3).

- **Selection:** the selection of physicians/practices/institutions will be performed based on availability of eligible patients. The selection process will be summarized by country in the study reports.
 - A physician can only participate in 1 wave of this study, and no more than 2 physicians from the same practice/institution can participate in each wave of this study.
 - Physicians who have participated in any randomized clinical trials with Praluent (alirocumab) will be excluded from this study.
- **Recruitment**: physicians will then be recruited remotely (over the phone or by e-mail) after the end of the 6-month observational period:

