 - The physician will be informed on the main purpose of the study, ie, assessing the effectiveness of the SmPC dosing recommendation to avoid very low LDL-C, collecting key characteristics and treatment approaches for Praluent-treated patients in a real world setting, and on the general design of the study (CRF, electronic platform). The physician will be informed that there is no need to interview his/her patients in order to conduct the study, except to get their consent in order to collect their data retrospectively, when informed consent is required by local regulation. Data availability from the 6-month observation period, and particularly critical variables such as LDL-C values, will be secured at the time of site selection through a questionnaire.
- A total of 20 physicians in Wave 1 and 61 physicians in Wave 2 were enrolled across all
 the participating countries. About 36 to 63 physicians are expected to be enrolled in
 Wave 3.

The detailed physician selection process will be described in a separate study plan which will be generated at study launch and updated during the conduct of the study, describing each wave separately.

It is likely that physicians who participate in this study may be different from those who do not with respect to specialty. It is anticipated that specialists are more likely to participate. The specialty, level of prescriptions, and reason for refusal (if available) will be described for the physicians who do not accept participation in the study.

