9.6.3 Site/Physicians questionnaire

Physicians who will not accept to participate will be described (specialty and level of prescriptions, reason for refusal, where available).

For physicians who will accept to participate, a physician questionnaire will be put in place to collect the physician's data mentioned in Section 9.3.1, and the potential availability of critical variables, such as LDL-C values, that need to be collected. An ad hoc question will be included in the Site Information Questionnaire used at Site Selection in order to qualify sites for participation.

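### The representativeness check in Section 9.7.3 sets a CRF-based prescription level against a database-identified population, without showing that the two measures are comparable

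*Protocol*

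**What the plan says.** Protocol Section 9.7.3, step a), names the source for participants: "The MAH will be collecting information on the level of prescription via a case report form (CRF) on the enrolled physicians". Section 9.6.3 gives the instrument for physicians who accept: "a physician questionnaire will be put in place to collect the physician's data mentioned in Section 9.3.1". Section 9.3 places this collection at recruitment, and Section 9.3.1 lists the variable without a count, reference period or cut-point.

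The comparison follows in the same step: "The final selected study sample of Praluent prescribers will be compared to the population of Praluent prescribers", that population being "identified from the Xponent or equivalent databases, with respect to the level of prescription".

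Section 9.2.4.1 describes how the databases are used. For sites, "prescribing volume of Praluent will be identified via Xponent database" or an equivalent source of pharmacy prescriptions. Then "physicians/practices/institutions (depending on each country's data privacy limitations) with Praluent prescription during the eligibility period will be identified via OneKey database" or a similar source. The same section deals with refusers: "The specialty, level of prescriptions, and reason for refusal (if available) will be described for the physicians who do not accept participation".

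Steps b) and c) of Section 9.7.3 depend on the comparison. If the high, medium and low groups are not similarly balanced and representativeness cannot be assumed, results are stratified by level of prescription in the interim and final reports. Statistical techniques may then be applied where judged appropriate.

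**The concern.** A check of this kind should isolate one thing: whether the physicians who took part differ from prescribers at large in how much they prescribe. If one side is classed from a questionnaire answer and the other from pharmacy records, any observed difference is the sum of selection and measurement, and the design cannot separate them. A source difference may suggest selection where there is none, or cancel a real imbalance.

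The check matters because amended protocol 01 dropped random selection of physicians and put an a posteriori assessment of prescription level in its place (Annex 3). Section 9.9 refers to Section 9.7.3 for this limitation. An error would reach the decision to stratify reports and, if step c) reweights, the adjusted estimates.

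**Working it through.** **Are the two measures aligned?**

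- *Source.* Participants: CRF or questionnaire (9.7.3 a, 9.6.3). Population: identified from pharmacy prescription databases (9.7.3 a, 9.2.4.1). That the population's level also comes from there is the natural reading, though not spelled out.
- *Unit.* Participants: the physician (9.3.1). Database: volume is described per site, and identification may be by physician, practice or institution.
- *Period.* The questionnaire is completed at recruitment and states no reference period. Section 6 puts Wave 1 eligibility at March to June 2017 and recruitment at Q2 2018 to Q1 2019; for Wave 3 the dates are July 2018 to June 2019 and Q1 2020 to Q1 2021.
- *Cut-points.* High, medium and low are named in 9.7.3 b) but not defined for either side.

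No section says that participants' database volume will be used for the comparison, or that the two sources will be checked against each other.

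**Illustration of size.** The plan has no figure to reproduce and gives no CRF-to-database agreement rate, so the shifts below are assumptions. Physician counts come from 9.2.4.1: 20 + 61 + 36 = 117 and 20 + 61 + 63 = 144.

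*False imbalance.* Take participants who truly match a population of one third per level, and let the CRF move 20% of low and of medium prescribers up one level:

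- low: (1/3)(0.8) = 26.7%
- medium: (1/3)(0.8) + (1/3)(0.2) = 33.3%
- high: 1/3 + (1/3)(0.2) = 40.0%

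The shift is 6.7 points at each end. The standard error of a one-third share is √[(1/3)(2/3)/n]:

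| Physicians | SE (points) | 6.7 / SE |
|---|---|---|
| 117 (pooled, low) | 4.4 | 1.5 |
| 144 (pooled, high) | 3.9 | 1.7 |
| 20 (Wave 1) | 10.5 | 0.6 |
| 61 (Wave 2) | 6.0 | 1.1 |
| 36 (Wave 3, low) | 7.9 | 0.8 |
| 63 (Wave 3, high) | 5.9 | 1.1 |

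If balance were judged by a 5% chi-square goodness-of-fit test with 2 df (an assumption; the plan names no test), upward shifts of 10%, 20% and 30% would flag this balanced sample with probability 11%, 33% and 66% at n = 117, and 13%, 40% and 75% at n = 144. For the 20% shift the per-wave probabilities are about 9% (n = 20), 13% (n = 36), 19% (n = 61) and 20% (n = 63).

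*Hidden imbalance.* Take a true participant split of 20/35/45 against one third each. With one source on both sides, the same test detects it with probability 86% (n = 117) to 92% (n = 144). If the CRF moves 20% of high and of medium prescribers down one level:

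- low: 20 + 0.2 × 35 = 27%
- medium: 0.8 × 35 + 0.2 × 45 = 37%
- high: 0.8 × 45 = 36%

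Detection falls to 24% to 29%.

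*Possible effect on step c).* If the technique were reweighting to population shares, the balanced sample above would get weights of 33.3/26.7 = 1.25 for low, 33.3/33.3 = 1.00 for medium and 33.3/40.0 = 0.83 for high, where none were needed.

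**The case against.** The strongest reply is that the mismatch is inferred. The protocol defines the level for neither side; cut-points, period and unit are ordinary SAP content, and 9.2.4.1 leaves selection detail to a separate study plan. Either document may already use the database value for participants. This stands to the extent that the measures cannot be said to differ, only that they are not shown to agree. It does not remove the point, because 9.7.3 a) itself names the CRF as the source for participants.

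A reader might infer that this is the only safeguard against physician selection. The documents do not support that. Section 9.2.2.2 excludes physicians from randomised trials of the drug and from previous waves, 9.2.4.1 describes refusers, 9.7.3 has a 15% rule for physicians in observational studies, and 9.9 promises efforts on specialty mix. The narrower statement holds: no other check compares the sample with the prescriber population on prescription level.

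A reader might also infer that the comparison mechanically decides stratification and correction. Step b) also requires a judgement that representativeness cannot be assumed, step c) is discretionary, and the lead-in to a) already announces stratification by usage pattern. A false alarm under b) alone would only add stratified tables.

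Nor is a like-for-like measure certain everywhere. Databases vary by country, and the level given for refusers has no stated source and is reported only where available (9.6.3). Where only site volume exists, classing a physician by it brings some misclassification of its own.

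Finally, the magnitude is assumed. Even the 20% shift stays below 1.96 standard errors for a single share.

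**Conclusion.** The point holds in limited form. As written, 9.7.3 a) can mix a measurement difference with selection on prescription level, in either direction, because the two sides are not shown to share source, period, unit or cut-points. The documents do not reveal the size. Under a one-directional 20% shift from an even three-way split, the apparent distortion is 6.7 points at each end, a modest signal when pooled and a weak one within a wave. The detection probabilities further assume a chi-square test that the plan does not name.

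It would be tempting to conclude that the main results are biased. They are not affected: the unadjusted proportions in Section 9.7.1 do not use prescription level. What is at risk is the reading of the representativeness check, the choice to stratify, and any adjusted estimate under c). Priority is minor to moderate.

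**What to change.** In Section 9.7.3 a), class both the enrolled prescribers and the source population as high, medium or low from the same database, over the same eligibility period, at the same unit and with the same cut-points, wherever the volume drawn at identification (9.2.4.1) exists. Use the site as the unit on both sides where privacy rules prevent physician-level data. Keep the CRF level as a description and report its agreement with the database level. State for which countries the common measure is missing.

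The cost is a wording change in 9.7.3 or the SAP and reuse of data already obtained to find sites; no further patient data are needed. The drawback is that classes in some countries will be site-level rather than physician-level, and that database coverage may vary between countries.
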